B2.1. PTSD, Cognitive Deficit, and ADHD: In our on-going project, we evaluated combat veterans with and without PTSD with Clinician Administered PTSD Scale (CAPS), Conners' Adult ADHD Rating Scales–Self Report: Short Version (CAARS–S:S, score > 65 is regarded clinical significant cognitive impairment; Conner et al 1999). We included 47 participants, 29 PTSD subject (13 with CAARS > 65, 45%) and 18 controls (2 with SAARS > 65, 11%). The results indicated PTSD diagnosis is associated with significantly higher self-reported attentional and executive dysfunction symptoms ($\chi^2 = 5.81, p = 0.16$). This was also evident in the significant correlations between CAPS and CAARS-S:S scores ($R=0.497, p < 0.01$), and CAPS PTSD symptoms ($\beta=.26, t=1.88, p=.05$), and PTSD patient cognitive deficit severity as measured by the CAARS-S:S ($\beta=.59, t=4.81, p<.001, R^2=.34$). These findings further support available literature suggesting that cognitive symptoms associated with PTSD diagnosis are highly correlated with patients' functional outcome.

B2.2. MPH Improves Cognitive Function: Further, we conducted additional preliminary analyses with 8 PTSD individuals with cognitive symptoms who were treated with MPH. Analyses conducted on clinical assessments of patients' PTSD and ADHD symptoms (CAPS and CAARS-S:S) before and after MPH treatment revealed significant reductions in both PTSD and self-reported cognitive deficit symptoms (see Fig1 and Fig2; $F(1, 7) = 22.39, p = .002$).

C. RESEARCH DESIGN AND METHODS:

C1. Overview: The proposed project is a pilot, feasibility double-blind crossover study to investigate the efficacy and safety of ATX with comorbid PTSD/ADHD patients to reduce cognitive symptoms, improve treatment retention and response, and improve patient's activities of daily living. A prospective, 10-week, fixed-dose, randomized, double-blind, placebo-controlled, and cross-over trial of ATX as an adjunctive medication to other therapies will be conducted among veterans with comorbid PTSD/ADHD. The short-duration, crossover design, and blind enable the study to be feasible in both time and funding level. **The Primary Objective** is to assess the efficacy of fixed dose of ATX (80mg) (compared with placebo) in reducing cognitive symptoms in comorbid ADHD/PTSD such that functional

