impairment and treatment retention are both improved, while **The Secondary Objective** is to replicate the our preliminary finding of negative impact of cognitive symptoms of ADHD on PTSD clinical outcomes. **The Tertiary Objective** is to assess the efficacy of ATX in reducing broad spectrum of PTSD symptoms. The proposed study will take 10 weeks and include two phases (**Phase I**: Initial Phase, 5 weeks; **Phase II**: Crossover Phase, 5 weeks). The crossover design was employed to both achieve study objectives while minimizing costs. Each phase consists two periods: **Period I** (week1 in Phase I and week6 in phase II) consist of psychological and physical assessments and placebo lead-in/wash-out, in which subjects take 6 days placebo; **Period II** (weeks 2-5 in Phase I and week7-10 in Phase II) consist of treatment with either atomoxetine 80mg daily or placebo daily). This project will take advantage of established on-going PTSD assessment and treatment clinical trials currently performed at the Ralph H. Johnson VA Medical Center (RHJVAMC) to facilitate recruitment. The proposed 50 veterans with ADHD/PTSD will be recruited from these on-going trials enabling both comprehensive assessment and evaluation of patients' engagement in ongoing PTSD treatments. Subjects will be randomized and assigned by the study investigator ([name]) into crossover group 1 (ATX at Phase I, then placebo at Phase II) or 2 (placebo at Phase I, then ATX at Phase II) with both placebo and medication administered through pharmacy. Subjects and other investigators are thus able to remain blinded to the order of treatment assignment throughout the study. The 1-week interval was based on published pharmacokinetic data for 4 week doses of ATX (*Witcher et al, 2003*). After crossover, patients will be unblinded and data will be cleaned and analyzed. Final follow up will be 30-days after last visit.

C2. Investigational Agent: ATX is a non-stimulant, FDA approved agent for treatment of ADHD. ATX 80mg is the most common adult dose used in ADHD with and without comorbid condition (Adler et al, 2009). In this project, 80 mg ATX and placebo will be prepared in capsules with identical appearance and similar taste by Eli Lilly and Company, Indianapolis, Indiana.

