Adverse effects (AE): Typical adverse events reported significantly more frequently with atomoxetine than placebo included dry mouth, insomnia, nausea, decreased appetite, constipation, dizziness, sweating, dysuria, sexual problems and palpitations. Modest increases in heart rate and blood pressure were well tolerated and gradually decreased on cessation of treatment.

Contraindications: ATX is contraindicated in patients known to be hypersensitive to the drug and during treatment with monoamine oxidase inhibitors (hypertensive crises may result). Medication will be stored and dispensed from the Charleston VAMC investigational drug pharmacy. Records will be maintained of all doses dispensed, and Veterans will be asked to return all unused tablets and empty prescription vials to the clinic for assessment of treatment compliance.

C3. Method

Subject Recruitment: All the subjects will be recruited through Charleston VAMC Mental Health Service Line. The Charleston VAMC has a large base of potential comorbid PTSD and ADHD participants. Many clinical trials, including pharmaceutical and psychotherapeutic trials are currently conducted in conjunction with the Charleston VAMC PTSD Clinical Team (PCT) clinic and the PCT team receives numerous PTSD evaluation consults from OIF/OEF program and Primary Care. Currently the PCT clinic receives 200 to 250 new referrals yearly of OIF/OEF Veterans who meet full criteria for PTSD based on a comprehensive initial intake interview that includes CAPS and functional impairment assessments. PI, [name] currently manages pharmacological consults for OIF and OEF Veterans. A HIPAA waiver of authorization will be on file with the IRB giving the research team permission to recruit from prior study populations. Veterans with PTSD from OIF/OEF are uniquely suited for this study because statistically they have fewer confounding variables for this clinical trial, including medical conditions such as hypertension or glaucoma and cognitive impairments such as dementia. Interested veterans who participate in clinical trials are explained the nature, purpose, and procedure of the study and asked to sign an informed consent that will explain in detail the purpose of the study, potential risks and benefits of pharmacotherapy study participation and alternative treatments that may be available.

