PTSD Medication Stabilization: Those patients meeting inclusion criteria will be asked to maintain medications at current dosages where medically possible. Participants who have not initiated new prescription medications in the previous 4 weeks will initiate treatment one week following the assessment battery. However, those potential participants who have recently begun trials of prescription medication will be required to wait 4 weeks post-assessment to ensure medication stabilization, at which point the assessment battery will be re-administered.

Efficacy Assessments and Outcome Measurement: Primary outcome measures will be conducted at baseline and all subsequent visits by a qualified research clinician using the CAARS-S:S, with the Barkley Adult ADHD Rating Scale-IV (BAARS-IV) and Adult ADHD Quality of Life-29 (AAQoL-29) conducted at follow up visits. Clinical Global Impression Severity (CGI-S, at baseline only) and Clinical Global Impression Improvement (CGI-I, at all visits except baseline and W1) will be done as well. Additional assessments for evaluating secondary outcomes will include the Clinician Administered PTSD Scale (CAPS), Hamilton Depression Scale (HAM-D). Quality of life will be assessed using the Veteran's version of the Medical Outcomes Study 36-Item Short-Form Health Survey (SF36-V). In addition to subjective measures, the response inhibition task Go/NoGo (GNG) and Stop Signal (SST) will be used as objective assessments to measure ATX treatment outcomes.

Key Assessment Measures:

Mini-International Neuropsychiatric Interview (MINI, Sheehan et al., 1998): The MINI is an abbreviated structured psychiatric interview that takes approximately 10-20 minutes to complete. The MINI has shown good inter-rater reliability and test-retest reliability for screening psychiatric disorders.

CAADID Part II: Diagnostic Criteria (CAADID, Epstein et al., 2001) The CAADID is a structured interview that assists in the process of diagnosing adult ADHD. This assessment is appropriate for those 18 and older. It is most effective when used with other types of ADHD measures, such as the CAARS™.

Clinician Administered PTSD scale (CAPS, Weathers et al., 2000): The CAPS is a structured interview that assesses both frequency and intensity of PTSD symptoms according to DSM-IV criteria. It provides both a dichotomous index for PTSD diagnoses and a continuous index of PTSD symptom severity.

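### An investigator who is by implication outside the blind assigns treatment sequence, with no generation or concealment method stated, and no data lock is placed before unblinding

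*Combined protocol and SAP*

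**What the plan says.** **Design label.** C1 describes "A prospective, 10-week, fixed-dose, randomized, double-blind, placebo-controlled, and cross-over trial of ATX".

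**Assignment.** C1 states "Subjects will be randomized and assigned by the study investigator" to one of the two sequences, "with both placebo and medication administered through pharmacy". From this it concludes: "Subjects and other investigators are thus able to remain blinded to the order of treatment assignment throughout the study".

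**Masking of the product.** In C2, active drug and placebo "will be prepared in capsules with identical appearance and similar taste". C2 also says: "Medication will be stored and dispensed from the Charleston VAMC investigational drug pharmacy". The pharmacy is given no role in producing or holding an allocation list.

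**Entry and rating.** Under Efficacy Assessments in C3: "Primary outcome measures will be conducted at baseline and all subsequent visits by a qualified research clinician using the CAARS-S:S". Under Diagnostic Procedures, a research assistant administers the diagnostic scales, and several investigators, the PI among them, settle the final diagnosis. Section B1 has co-investigators help with statistical analysis, assessment and recruitment.

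**End of the blind.** C1 states: "After crossover, patients will be unblinded and data will be cleaned and analyzed".

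**The concern.** Allocation concealment and blinding are separate protections. Matched capsules and pharmacy dispensing keep participants and staff from learning what was given. They do nothing to hide the *next* assignment from the person who makes it. If that person also has a say in who is entered, or when, the two sequence groups can differ at entry for reasons other than chance. If that person also rates, scores that depend on an interviewer's judgement are open to influence.

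The unblinding sentence raises a second, smaller question. If the code were open to those who clean or analyse before the data are fixed, decisions on exclusions, scoring and missing values could be made with sequence known. A stated lock removes that possibility, and the plan states none.

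**Working it through.** No arithmetic can size this. The check is a comparison of the relevant text, plus one count.

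**1. Who is inside the blind.** C1 names one investigator as the assigner, then extends the blind to participants and the *other* investigators. That word leaves the assigner out. This is an inference; the plan never says outright that the assigner is unblinded.

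**2. Is a method given?** The word *randomized* occurs twice, both times in C1. Neither place, nor any other section, gives a generation method, allocation ratio, blocking, stratification, concealment step or list holder.

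**3. Could the assigner affect entry?**
- Limits on influence: Screening/Baseline Evaluation in C3 sets numeric thresholds (CAARS-S:S of 65 or higher, CAPS total of 55 or higher, at least 6 months of PTSD), and the final diagnosis is shared among several investigators.
- Room that remains: good physical health and whether a depressive episode is secondary to PTSD are judgements, and the 4-week wait after a recent prescription affects timing.
- Nothing separates the assigner from these decisions. The names that would show whether the roles overlap are removed from the text available here.

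**4. Is a lock described?** The word *locked* occurs four times: once in section 1.1 (an office), once in 1.2 (cabinets) and twice in 1.5 (cabinets and an area). All four concern physical storage. Sections 1.2 and 1.5 also say that data are coded by identification number, with the data coordinator holding names and codes. That protects identity and does not hide sequence. The only blind stated specifically for data or laboratory work is for genotyping (Database Management in C3, and 1.5).

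**5. Where any bias would act.** Write a participant's own level as m, the treatment effect as t, and the phase effects as p1 and p2. Assume no carryover.
- ATX first: ATX minus placebo = (m + p1 + t) − (m + p2) = t + (p1 − p2).
- Placebo first: ATX minus placebo = (m + p2 + t) − (m + p1) = t − (p1 − p2).

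The level m cancels for anyone with both phases, so a difference in level between the sequence groups does little harm in a within-participant comparison of completers. A participant who leaves before Phase II contributes no such difference, and m does not cancel. The Statistical Analyses section enters treatment as a between factor, so this cancellation is a favourable assumption about the eventual analysis.

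**6. How many participants.** Statistical Analyses plans up to 50 enrolled for 40 completers: 50 − 40 = 10, and 10/50 = 20%. Some of these may leave before randomization and others during Phase II, so 10 is the planned ceiling for those leaving between randomization and Phase II.

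**7. Which measures.** CAARS-S:S and AAQoL-29 are self-reported (Key Assessment Measures). CAPS is a structured interview and would be more exposed if the assigner also rated.

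**The case against.** The strongest reply has four parts.

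*The pharmacy and the matched capsules already protect the trial.* They do so after assignment, for participants and blinded staff. They do not conceal an upcoming assignment from the assigner, so this answers only part of the point.

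*Numeric thresholds and shared diagnosis leave little room to steer entry.* This largely stands as to who enters. It is weaker as to when, and the plan still sets no bar.

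*Role overlap is a product of redaction.* A reader might infer that the assigner recruits, diagnoses or rates. The document does not support that: the assigner and the diagnosing investigators are all unnamed here, and someone with the full text may be able to settle it. What stands is that no rule separates the roles.

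*The unblinding sentence is about patients.* A reader might infer that the plan is to clean and analyse with sequence known. The text does not say so. Its subject is patients, its clauses are joined by *and* with no explicit order for staff, and C1 elsewhere keeps the other investigators blinded throughout the study. The co-investigator who helps with analysis may be covered by that. Whether it extends to cleaning and analysis is unclear, as is whether unblinding is participant by participant or study-wide. What stands is an ambiguous sentence and an unmentioned lock.

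**Conclusion.** The point holds as a minor one. C1 states a procedure that is weaker than it need be: an investigator, by implication unblinded, assigns sequence with no stated generation or concealment method. It also names unblinding of patients ahead of cleaning, with no lock described.

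The conclusion rests on two readings: that *other* excludes the assigner, and that silence on method, list custody and lock means that none is specified in this plan. It does not rest on any showing that roles overlap or that data will be handled unblinded. Nor does it follow that the trial fails to be double-blind for participants and for staff other than the assigner.

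No bias can be computed. The most exposed are participants who leave between randomization and Phase II (at most 10 of 50 under the plan's allowance) and interviewer-rated measures, the latter only if the assigner rates.

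**What to change.** **Assignment.** State how the sequence is generated. Have the investigational pharmacy, which already stores and dispenses both products, or another person with no participant contact, hold a computer-generated list. Make each assignment only after eligibility is confirmed and the participant is entered. Give no list access to anyone who enrols, diagnoses, rates, cleans or analyses.

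**Unblinding.** Reword the C1 sentence so that efficacy data through week 10 are cleaned and locked before the code is opened to staff or analysts, study-wide, after the last participant's week-10 visit. If participants are to learn their own sequence sooner, the pharmacy can tell them once their own week-10 data are locked, without disclosing it to staff who enrol, rate or analyse. Opening codes to staff one participant at a time during enrolment would expose past assignments. If randomization is blocked, these help to predict later ones: under a fixed ratio with known block size, the last assignment in a block follows from the others.

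**Cost.** Protocol wording, and list custody for the pharmacy or other holder. Sample size, visits and drug supply do not change. Staff unblinding waits until the last week-10 data are locked; the document gives no accrual period, so that wait cannot be sized. The change gives full protection only if adopted before the first assignment.

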Inclusion Criteria: 1) OIF/OEF Veterans age 20 to 60 with PTSD and significant ADHD symptoms (CAARS-S:S > 65); 2) Good physical health. 3) Trauma exposure sufficient to meet Category A of PTSD criteria (Breslau and Kessler 2001)

Exclusion Criteria: 1) Age younger than 20 or greater than 60. 2) Known sensitivity to ATX. 3) Presence of disorders that could conceivably be exacerbated by atomoxetine (specifically, narrow

angle closure glaucoma, urinary outflow obstruction, hypertension, and neurological disorders, particularly tics and Tourette's syndrome, or a history of epilepsy or seizures). 4) use of concomitant medication that could potentially interact with atomoxetine including monoamine oxidase inhibitors (MAOI), antihypertensive medication, or any concomitant medication that was a cytochrome 2D6 inhibitor (CYP2D6) as atomoxetine's elimination involves the CYP2D6 system. 5) An active or lifetime major mental health diagnosis as determined by DSM-IV Axis I Disorders, including schizophrenia, schizoaffective disorder, psychotic disorder not otherwise specified, bipolar I disorder, bipolar II disorder, bipolar disorder not otherwise specified. The project will allow presence of depressive disorders if the depressive episodes are secondary to PTSD. 6) Current substance dependence and abuse (within 3 month). 7) Females who are pregnant or likely to become pregnant. 8) Active suicidal thoughts and behavior.

Suicide Screen: A screen for recent or current suicidal thought and/or attempts will be conducted before the interview. If a subject reports suicidal thought at the time of interview, his physician or psychiatrist will be informed and the subject will be escorted to the ER immediately for further evaluation and treatment.

Screening/Baseline Evaluation: During this visit subjects will review and sign the Informed Consent. Eligibility to participate in this portion of the study will be determined by a minimum 6-month duration of PTSD illness, CAARS-S:S score of 65 or higher as well as a positive ADHD score for the adult section of the Conners ADHD interview, a total CAPS severity score of 55 or higher at the baseline visit. If the subjects qualify, then a medical/psychiatric history will be obtained along with laboratory safety measures, including electrocardiogram (EKG), liver and renal panel (SMA-12), complete blood count with differential, urine toxicology screen and concomitant meds. If the veteran is female, urine pregnancy test will be obtained.

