Concom meds	X	X	X		X	X		
AEs			X			X		

Safety assessments: At each study visit, safety will be assessed by measuring: weight, sitting blood pressure, heart rate, adverse events (except baseline), and use of concomitant medications. Laboratory and EKG assessments will be performed at baseline, one and seven weeks. Anxiety, depression, and suicidal ideation will be assessed with Ham-A, Ham-D, and suicide screen in each of the visits. Compliance will be assessed by pill counts and appointment attendance. Referrals to the Charleston PTSD clinic will be conducted at the final study visit for any remaining PTSD symptoms and the CBT clinic for remaining ADHD symptoms.

Follow-up: The final visit, 30-days after study completion, will include safety assessments, along with follow-up of any unresolved adverse events. This visit will also provide assurance that veterans who participated in this medication study will have adequate follow-up care in the Charleston VAMC PTSD or Mental Health Outpatient Clinic either with continued medication or psychotherapy. This visit may be done over the phone or by mail.

Diagnostic Procedures: After obtaining the informed consent, a trained research assistant will perform the initial interview and administer all of the diagnostic scales to the participants. [name], [name] (MD, Co-Investigator) and [name] (PI) will make the final diagnosis based on all the data collected. The DSM-IV diagnostic criteria will be used to ascertain each phenotype.

Database Management: All collected clinical, demographic, and geographic data will be stored in Research Database Storage in the Charleston VAMC PTSD Program. The genotyping data will be stored in [name] laboratory Research Database. For each patient, the clinical database will provide information as following: age, gender, ethnic origin, medical and psychiatric diagnosis, family history, developmental history, and existence of comorbidity. The genotyping data will be separately entered without knowledge of clinical data. Strict confidentiality is maintained regarding database information, which is secured and for research purposes only. All the specimens from the subjects will be labeled by code at the clinic. Names will not appear on specimens, nor will they be available in the laboratory. The person conducting the genotyping is blind to the clinical profile of the subject. No names or identifiable information will be used in any data presentation.

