1.1 Risks to Subjects

a. Human Subjects Involvement and Characteristics:

Totally, up to 50 veterans with comorbid ADHD and PTSD will be recruited for this pilot clinical trial. All subjects will be Veterans from Operation Iraq Freedom / Operation Enduring Freedom (OIF/OEF). Our record review showed age range from 20 to 60 in this OIF/OEF group, and statistically they have fewer confounding variables for this clinical trial, including medical conditions such as hypertension or glaucoma (described detail in exclusion criteria) and cognitive impairments such as dementia, which meet criteria for our research study. PTSD subjects with and without ADHD cognitive symptoms will be recruited from the Charleston VAMC Mental Health Service Line. Examining and treatment of ADHD cognitive symptoms among Veterans with PTSD is scientifically and ethically justified to further understand the mechanism of developing PTSD after trauma exposure, and what is the best treatment for Veterans with comorbid PTSD and ADHD. Specific inclusion and exclusion criteria are listed below:

Inclusion Criteria: 1) OIF/OEF Veterans age 20 to 60 with PTSD and significant ADHD symptoms (CAARS-S:S > 65); 2) Good physical health. 3) Trauma exposure sufficient to meet Category A of PTSD criteria (Breslau and Kessler 2001)

Exclusion Criteria: 1) Age younger than 20 or greater than 60. 2) Known sensitivity to ATX 3) Presence of disorders that could conceivably be exacerbated by atomoxetine (specifically, narrow angle closure glaucoma, urinary outflow obstruction, hypertension, and neurological disorders, particularly tics and Tourette's syndrome, or a history of epilepsy or seizures). 4) use of concomitant medication that could potentially interact with atomoxetine including monoamine oxidase inhibitors (MAOI), antihypertensive medication, or any concomitant medication that was a cytochrome 2D6 inhibitor (CYP2D6), since atomoxetine's elimination involves the CYP2D6 system. 5) An active or lifetime major mental health diagnosis as determined by DSM-IV Axis I Disorders, including schizophrenia, schizoaffective disorder, psychotic disorder not otherwise specified, bipolar I disorder, bipolar II disorder, bipolar disorder not otherwise specified. The project will allow presence of depressive disorders if the depressive episodes are secondary to PTSD. 6) Current substance dependence and abuse (within 3 month). 7) Females who are pregnant. 8) Suicidal thoughts and behavior.

b. Sources of Material

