1.5 Data and Safety Monitoring

All collected clinical, demographic, and geographic data, as well as genotyping data will be stored in Psychiatric Genetic Research Database, a branch of Psychiatric Data Management. We will use computerized systems to collect, create, modify, maintain, archive, retrieve, and transmit clinical data. The genotyping data will be separately entered without knowledge of clinical data. Data of cortical inhibition will be stored in Charleston VAMC TMS Laboratory data bank.

All assessment information will be considered confidential. Data will be organized in code-labeled binders and stored in locked cabinets. Identification numbers will code data entered for computer analysis, and the data coordinator will keep all names and code numbers in a separate locked area. Findings will be made available to legitimate agencies, such as local IRB, and related research personnel. No names or identifiable information will be used in any data presentation. Strict confidentiality is maintained regarding database information, which is for research purpose only. All the specimens from the subjects will be labeled by code at the clinic. Names will not be used on specimens nor available in the research laboratory. The person conducting the sequencing and genotyping is blind to the clinical profile of the subject.

2 Inclusion of Woman and Minorities

Charleston VA Medical Center has traditionally served Veterans both in Charleston as well as neighboring counties. With the exception of occasional out-of-state referrals, the population served reflects that of the Charleston metropolitan area. Participation in this research is open to all Veterans who meet eligibility criteria regardless of race, gender, ethnicity, or socioeconomic status. We expect PTSD to affect Veterans of all races and ethnicities across a range of socioeconomic status. We had approximately 35% African American participants in our previous recruitment, which is proportional to our surrounding area. As for male to female ratio, our previous studies have shown a higher incidence of PTSD in male Veterans because a higher percentage of male soldiers have participated in combat. We expect a greater percentage of female Veterans from Iraq Freedom Operation and Afghanistan given we have found that more female soldiers have participated in the two wars. All possible effort will be made to recruit female Veterans.

3 Inclusion of Children

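### The only pregnancy test the plan states is at screening, so placebo-first women start atomoxetine 6 to 7 weeks after it with no stated repeat

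*Combined protocol and SAP*

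**What the plan says.** **The test.** C3, Screening/Baseline Evaluation, lists the laboratory safety measures in one sentence and then adds, in a separate one: "If the veteran is female, urine pregnancy test will be obtained". No other section of the supplied text states a pregnancy test.

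**The exclusion.** It appears in two forms. Exclusion 7 in C3 reads "Females who are pregnant or likely to become pregnant". The list in section 1.1 of the Human Subjects part has only "Females who are pregnant. 8) Suicidal thoughts and behavior" for exclusions 7 and 8, without the forward-looking words.

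**The schedule.** C1 defines crossover group 2 as "placebo at Phase I, then ATX at Phase II". Weeks 1 and 6 are placebo lead-in or wash-out; weeks 2 to 5 and 7 to 10 are treatment. Table 1 marks the Labs, EKG row at Screening/Baseline, W2 and W7, and marks dispensing at W1, W2, W6 and W7. It has no pregnancy-test row. C3, Safety assessments, says "Laboratory and EKG assessments will be performed at baseline, one and seven weeks" and does not list what the laboratory work contains.

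**Time before treatment.** Under C3, PTSD Medication Stabilization, participants with no new prescription in the previous 4 weeks "will initiate treatment one week following the assessment battery". Those with a recent change wait 4 weeks, "at which point the assessment battery will be re-administered". The contents of that battery are not defined.

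**Women in the trial.** Section 2 states: "All possible effort will be made to recruit female Veterans".

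**The concern.** The sponsor chose to keep pregnant women out and to test for pregnancy at entry. In a parallel-group trial, an entry test would usually fall close to the first dose. Here the crossover puts a full placebo phase and a wash-out between the test and the first atomoxetine dose for one of the two sequences. A negative result at screening says nothing about a conception during that time.

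If the W2 and W7 laboratory work does not include the test, a site that follows the plan exactly could give 80 mg atomoxetine to a woman whom the plan means to exclude. This is a participant-safety point. It does not touch the sample size, the analysis or the treatment comparison.

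**Working it through.** **Inputs.** From C1: lead-in 1 week, Phase I treatment 4 weeks, wash-out 1 week, Phase II treatment 4 weeks. From C3, PTSD Medication Stabilization: 1 week from battery to treatment on the ordinary path, and a 4-week wait after a recent medication change.

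**The plan's own figure.** 1 + 4 + 1 + 4 = 10 weeks, which matches the stated study duration.

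**Test to first atomoxetine dose.** Let *g* be the weeks from the baseline test to the start of W1. If the stated one week runs to active treatment at W2, *g* = 0. If it runs to the placebo lead-in at W1, *g* = 1. Let *s* be the stabilization wait (0 or 4 weeks).

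- Atomoxetine-first: *s* + *g* + 1
- Placebo-first: *s* + *g* + 1 + 4 + 1 = *s* + *g* + 6

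| Path | Atomoxetine-first | Placebo-first |
|---|---|---|
| Ordinary (*s* = 0) | 0+1 to 1+1 = 1–2 weeks | 0+6 to 1+6 = 6–7 weeks |
| 4-week wait, test not repeated (*s* = 4) | 4+0+1 to 4+1+1 = 5–6 weeks | 4+0+6 to 4+1+6 = 10–11 weeks |
| 4-week wait, test repeated with the battery | 1–2 weeks | 6–7 weeks |
| Test at W2 and W7 before dispensing | about 0 | about 0 |

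**Do the W2 and W7 labs include the test?** The text does not settle this.

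- Against inclusion: the screening text gives the pregnancy test its own sentence after the list of laboratory measures.
- Against inclusion: the urine toxicology screen is in that list. If the UDS row in Table 1 is that screen, it is tracked separately, at baseline and W5, and not at W2 or W7. So the Labs, EKG row cannot be assumed to repeat every baseline test.
- For inclusion: Table 1 has no pregnancy-test row even at baseline, where the test is certainly done, so it may sit inside another row.
- Safety assessments names no contents. It times the first repeat at week one where Table 1 marks W2. The two agree on W7, the visit that matters for the placebo-first sequence.

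On balance the more natural reading is that the test is not repeated, but it is a reading and not a statement in the plan.

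**The case against.** The case on the other side has four parts.

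1. **The labs may already cover it.** The Labs, EKG row is marked at W2 and W7, the visits at which treatment supplies are dispensed. If the test is part of it, the gap is about 0 in both sequences. This stands as a possibility, and it is why a clarification may be all that is needed. A reader might infer that the plan definitely omits a repeat test; the documents show only that none is stated.

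2. **The text is incomplete.** Consent pages are not in the supplied text and could hold contraception or pregnancy instructions. This also stands, and it limits the point to the methods text and the schedule.

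3. **Women likely to become pregnant are excluded.** The C3 wording looks past the day of the test and so lowers the risk. It remains a judgement at entry with no stated criteria, and section 1.1 leaves it out. It covers the gap only in part.

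4. **No pregnancy risk is documented.** The adverse-effect and contraindication text (C2 and section 1.1) describes none, so a reader who infers demonstrated fetal harm goes beyond the documents. The argument rests on the sponsor's own exclusion and the small cost of a check. Nor do the documents establish how many women will take part: section 2 promises recruitment effort, not enrolment, and ages 20 to 60 include women who cannot conceive.

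**Conclusion.** The point holds at low severity. One pregnancy test is stated, at screening. Placebo-first women reach their first atomoxetine dose 6 to 7 weeks later on the ordinary path, against 1 to 2 weeks for atomoxetine-first. The placebo-first gap becomes about 10 to 11 weeks if a stabilization wait applies and the test is not repeated with the battery. The plan does not show that its pregnancy exclusion is checked again before atomoxetine starts.

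The figures assume that the visits run on schedule and that W1 begins 0 to 1 week after the battery. A reader might put the lower end of the stabilization path at 9 weeks by starting active treatment on the day the battery is re-administered. That drops the interval between battery and treatment, for which the text gives no support.

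No number of expected pregnancies can be given, because the number of women is not stated. Nothing here bears on the validity of the efficacy comparison.

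**What to change.** Add a row to Table 1: urine pregnancy test, for women who can become pregnant, at W2 and W7 in addition to baseline. Apply it in both sequences alike, since testing only those about to start atomoxetine would reveal the allocation. Require a negative result before the treatment supply is dispensed, and stop study drug on a positive result. Because these tests fall at the start of each treatment period, they close the gap whether or not the stabilization battery repeats the baseline test. They do not detect a conception during the 4 weeks on drug.

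Use the C3 wording of exclusion 7 in section 1.1.

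The cost is one table row, a sentence or two, and at most two extra urine tests per such woman, at visits already scheduled for labs and dispensing. No visit is added. If the W2 and W7 labs already include the test, a footnote to Table 1 saying so is enough, together with the wording change in section 1.1.
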